## **2.3. Benefit/Risk assessment**

GSK has included provisions in this trial to ensure participant's safety. Safety monitoring has been and will be conducted throughout this study by an unblinded Independent Data Monitoring Committee (IDMC) and by the Sponsor. The study includes the establishment of a surveillance system which may facilitate detection of respiratory tract infections, in particular lower respiratory tract **illness** (LRTIs) in infants enrolled in the study. Measures to suspend the study should a potential safety issue be identified are described in Section 8.2.3.

***In February 2022, the Independent Data Monitoring Committee (IDMC) for the RSV MAT-009 study observed an imbalance in the proportion of preterm births in the active versus the placebo group and recommended that study enrollment be paused. As a result, GSK voluntarily paused the enrollment, randomization, and vaccination of participants in its active pregnant women studies to investigate this safety signal.***

***Following a review of additional unblinded data from the RSV MAT-009 study, the imbalance in preterm births was noted to persist across a range of risk factors. A higher proportion of neonatal deaths reported in the active group compared to the placebo group was also observed. GSK then decided to stop enrollment and vaccination in all ongoing trials of RSV Maternal Vaccine (RSVPreF3) as a precautionary measure.***

***The observed numerical imbalance in neonatal deaths is not an independent safety signal but a consequence of the validated signal of preterm birth. No numerical imbalance in neonatal deaths was observed in the cohort of infants born at term. An in-depth qualitative review of the clinical information available for each neonatal death concluded that the events leading to neonatal death (e.g., very low or low birth weight, sepsis, necrotizing colitis, pneumonia, respiratory distress syndrome, hypoxic-ischemic injury) are commonly observed in preterm-born infants, particularly those who are extremely and very preterm, and there is no consistent temporal pattern of events from birth or from maternal vaccination.***

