*In January 2023, following assessment of the Study Day 43 post-birth interim analysis (DLP 04 October 2022) with data from 5328 maternal participants (3557 in the active group) and 5235 infant participants (3496 in the active group), the imbalance in preterm birth remains statistically significant (RR 1.38 (95% CI 1.08, 1.75); p value: 0.0090) and persists across a range of risk factors. The overall incidence of preterm birth in the study is low in both groups and remains below the preterm birth background rates for the majority of the participating countries. The imbalance in preterm births was observed more with low and middle-income countries (RR: 1.57, 95% CI: 1.17–2.10) than high-income countries (RR: 1.04, 95% CI: 0.68–1.58). In low and middle-income countries, the preterm birth imbalance peaked from August to December 2021 and was not observed consistently from January 2022 onward.*

*GSK concluded that preterm birth is an identified risk for the pregnant women population, for the RSV Maternal vaccine candidate. GSK has discontinued the work on this RSV maternal candidate vaccine and is closing out all ongoing trials. Additionally, GSK continues to monitor and follow up those participants immunized in the trials. Another study (RSV MAT-015) has been initiated to describe the safety of study participants who received RSVPreF3 maternal vaccination (any dose) or control in previous RSV MAT studies, including the RSV MAT-009 study, during any pregnancy conceived post-vaccination or post-control.*

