## 4. STUDY DESIGN

### 4.1. Overall design

The study is a Phase III, double-blind, randomized, placebo controlled, multi-centric, multi-country study with 2 parallel groups. At least 20% of participants will be enrolled at centers in the U.S.

The study design is adaptive, with recruitment and randomization occurring in 2 sequential stages, A and B. Stage B may begin immediately after the last participant is randomized in Stage A.

To encourage participation in the study and to achieve recruitment targets on time, the study sites will be encouraged to manage recruitment plans using methods that are acceptable within local regulations such as advertisements in news media and/or use of posters and fliers. All such recruitment materials will be approved by the local ethics committees.

Following verification that inclusion/exclusion criteria are met, all maternal participants will be randomized 2:1 to receive either GSK Biologicals’ RSV Maternal (RSVPreF3) vaccine or the placebo control.

Study procedures in Stage A differ from those in Stage B in 2 ways.

[figure not shown]
During Stage A only:

- All maternal participants will be asked to report solicited events during the 7 days post-dose, and
- Maternal and (as yet unborn) infant participants will be further randomized into sub-cohorts for blood sample collection for the assessment of immune response.

Figure 1 and Figure 2 provide overviews of the study design for maternal and infant participants, respectively.

Section 1.3 provides Schedules of Activities (SoAs) for maternal and infant participants. Section 9.5.1 describes the sequence of analyses for maternal and infant participant data.

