5.4. Analysis of safety and reactogenicity

5.4.1. Analysis of safety and reactogenicity planned in the protocol

Safety analyses in **maternal participants** will include summaries by study group and age category (18-34, 35-39, ≥ 40 years of age; overall) of solicited administration site and systemic events (for stage A subjects), unsolicited AEs, MAEs, SAEs, MA-RTIs (RSV-associated MA-RTIs and all-cause MA-RTIs), AEs leading to study withdrawal, pregnancy outcomes and pregnancy related AESIs.

Safety analyses in **infant participants** will include summaries by study group, overall and gestational age at birth (≥ 37 weeks or < 37 weeks) of neonatal AESIs, MAEs, SAEs, AEs leading to study withdrawal, and the occurrence of RSV-associated RTIs, LRTIs, severe LRTIs, RSV-associated hospitalizations, all-cause RTI and all-cause LRTI.

Safety analyses for maternal participants and infants may also be reported by economic region (LMIC and HIC).

Analyses of solicited AEs will be performed on the Solicited Safety set (maternal participants only). Analyses of unsolicited AEs will be performed on the ES.

Primary Safety Endpoints – Infant Participants	Statistical Analysis Methods

Occurrence of SAEs, AEs leading to study termination and medically attended AEs from birth up to 6 months after birth
 
Occurrence of SAEs, AEs leading to study termination and medically attended AEs from birth up to 12 months after birth.
	
CCI

Secondary Safety Endpoints – Maternal Participants	Statistical Analysis Methods

Occurrence of solicited injection site and systemic events in Stage A participants during a 7-day follow-up period after vaccination (i.e. the day of vaccination and 6 subsequent days).
	
CCI

Occurrence of unsolicited adverse events (AEs) in all maternal participants during a 30-day follow-up period after vaccination (i.e. the day of vaccination and 29 subsequent days).
	

	CCI

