
Pregnancy outcomes from Day 1 (Visit 1) up to 6 weeks after delivery (Day 43 post-delivery, Visit 4). These include live birth with no congenital anomalies, live birth with minor congenital anomaly(ies) only; live birth with at least one major congenital anomaly, fetal death/still birth (antepartum or intrapartum) with no congenital anomalies, fetal death/still birth (antepartum or intrapartum) with minor congenital anomalies only, fetal death/still birth (antepartum or intrapartum) with at least 1 major congenital anomaly; elective/therapeutic termination with no congenital anomalies; elective/therapeutic termination with minor congenital anomalies only, and elective/therapeutic termination with at least 1 major congenital anomaly.
	

Pregnancy-related adverse events (AEs) of special interest from Day 1 (Visit 1) up to 6 weeks after delivery (Day 43 post-delivery, Visit 4). These include maternal death, hypertensive disorders of pregnancy (gestational hypertension, pre-eclampsia, pre-eclampsia with severe features including eclampsia), fetal growth restriction, pathways to preterm birth (premature preterm rupture of membranes, preterm labor, provider-initiated preterm birth), gestational diabetes mellitus, chorioamnionitis.
	

Occurrence of serious adverse events (SAEs), AEs leading to study termination, and medically attended AEs in all maternal participants from Visit 1 (Day 1) up to 6 months after delivery.
	

Secondary Safety Endpoints – Infant Participants
	

The occurrence of neonatal AEs of special interest (reported up to 6 weeks after birth). These include small for gestational age, low birth weight including very low and extremely low birth weight (<2500 g, <1500g, <1000g), congenital anomalies (major external structural defects, internal structural defects, functional defects), neonatal death (in an extremely pre-term birth ($22 \leq GA < 28$ weeks), in a preterm live birth ($28 \leq GA < 37$ weeks), or in a term live birth), preterm birth.
	

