8. CHANGES FROM PLANNED ANALYSES

- By-participant listings of SAEs, AEs leading to study withdrawal, MAEs, adverse pregnancy outcomes and pregnancy related AESIs will be prepared and released. Such listings have already been released in earlier analyses. Due to study enrolment/vaccination stop, the study has been unblinded already before the final analysis.
- A sensitivity analysis for immunogenicity results excluding participants from Bangladesh, for which HIV testing was not performed before their enrollment into the study, has been added.
- Between group evaluations for immunogenicity analysis was clarified to be performed among RSV MAT and Control instead of vaccination groups, the wording has been corrected.
- In February 2022, enrollment and vaccination were stopped because of an imbalance in preterm births and associated neonatal deaths observed between the RSVPreF3-Mat and placebo groups. Subsequently the study was unblinded, and therefore the presented VE endpoints are descriptive.
- Subgroup analyses by economic region (LMIC and HIC) will be performed for demography, efficacy, and safety evaluations.
- Subgroup analyses by gestational age at birth will be performed for demography and safety evaluations.
- Sensitivity analysis for primary efficacy endpoints by using a negative binominal regression model have been removed.

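### Infant safety tables compare arms within term and preterm births, a post-randomisation split that the vaccine shifts, and Protocol 2.3 rests its neonatal-death statement partly on the term half

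*SAP*

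**What the plan says.** SAP 5.4.1 states that the infant safety analyses "will include summaries by study group, overall and gestational age at birth", with categories of 37 weeks or more and under 37 weeks. The split applies to neonatal AESIs, MAEs, SAEs, withdrawals and respiratory illness, not only to deaths. SAP 8 lists it as a change from plan: "Subgroup analyses by gestational age at birth will be performed for demography and safety evaluations". The neonatal-death endpoint is itself defined by category: extremely preterm, preterm, "or in a term live birth), preterm birth". The cells that describe the statistical methods are redacted.

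Protocol 2.3 gives the vaccine's effect on the splitting variable, "RR 1.38 (95% CI 1.08, 1.75); p value: 0.0090", and concludes: "GSK concluded that preterm birth is an identified risk for the pregnant women population". On deaths it reports a higher proportion in the vaccine arm and then states: "The observed numerical imbalance in neonatal deaths is not an independent safety signal but a consequence of the validated signal of preterm birth". Two supports follow: term-born infants showed no excess of deaths, and a qualitative review of the individual deaths found events typical of prematurity. No death counts, risk ratio, interval or mediation analysis is given.

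**The concern.** Protocol 4.1 says that "all maternal participants will be randomized 2:1". That makes the arms comparable at baseline, and the comparison of all infants inherits this. It does not carry over to groups defined by something that happens after vaccination and that vaccination changes. If vaccination turns some term births into preterm births, those infants leave the vaccine-arm term stratum and join the vaccine-arm preterm stratum, while their placebo counterparts stay at term. The two arms then hold different kinds of infant within each stratum, and a difference, or the lack of one, can arise from that sorting alone.

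Neither document carries a visible warning. The caution in SAP 6 concerns immunogenicity comparisons. SAP 7.1 sends the final analysis to public disclosure and the study report, where unlabelled term and preterm tables by arm may be read as randomised comparisons. Protocol 2.3 already uses one such comparison to support a firm causal statement.

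**Working it through.** **Inputs.** Preterm RR and interval: Protocol 2.3, quoted above. Infants at the Day 43 interim: "5235 infant participants (3496 in the active group", so 5235 − 3496 = 1739 on placebo. I assume that these are the denominators of the RR. The documents give no death counts, so every fatality figure below is an assumption.

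**1. Reproduce the stated p value.** SE(log RR) = [ln 1.75 − ln 1.08]/(2 × 1.96) = 0.1231. z = ln 1.38/0.1231 = 2.616, two-sided p = 0.0089. Rounding of the printed RR and limits allows 0.0072 to 0.0109, so the stated 0.0090 fits. Inverse-variance pooling of the two income-region RRs (1.57 and 1.04, with their intervals) gives 1.37 (1.08 to 1.75), which agrees.

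**2. Implied preterm counts.** Let a and b be the preterm births on vaccine and placebo. From the RR, a = 1.38 × (3496/1739) × b = 2.774b. From the SE, 1/a − 1/3496 + 1/b − 1/1739 = 0.1231². Solving gives b ≈ 85 (4.9%) and a ≈ 236 (6.7%). Rounding allows 4.7–5.0% and 6.5–6.9%.

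**3. Excess preterm births.** At the placebo rate the vaccine arm would have 3496 × 85/1739 = 171. The excess is 236 − 171 = 65, and 65/236 = 28%. The share depends on the RR alone: 0.38/1.38 = 28%. At the confidence limits it is 0.08/1.08 = 7% and 0.75/1.75 = 43%.

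**4. Preterm stratum, no direct effect on death.** Assume that the vaccine moves births only from term to preterm. Let the shifted infants' fatality be k times that of the other preterm infants. The apparent death RR is (1 + 0.38k)/1.38.

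| k (assumed) | 0 | 0.25 | 0.5 | 1 | 2 |
|---|---|---|---|---|---|
| Apparent RR | 0.72 | 0.79 | 0.86 | 1.00 | 1.28 |

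**5. Term stratum, no direct effect.** The shifted infants correspond to (0.0674 − 0.0488)/(1 − 0.0488) = 2.0% of the placebo term stratum. Let their mortality, had they been born at term, be k times that of other term infants. The apparent RR is 1/[1 + 0.0195(k − 1)].

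| k (assumed) | 1 | 2 | 5 | 10 | 20 |
|---|---|---|---|---|---|
| Apparent RR | 1.00 | 0.98 | 0.93 | 0.85 | 0.73 |

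**6. Information at term.** The term strata hold about 3496 − 236 = 3260 and 1739 − 85 = 1654 infants. For a true doubling of term neonatal mortality (power is a normal approximation, rough at these counts):

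| Placebo term mortality (assumed) | Expected deaths, vaccine vs placebo | Power | Chance that vaccine rate is no higher |
|---|---|---|---|
| 0.05% | 3.3 vs 0.8 | 6% | 21% |
| 0.1% | 6.5 vs 1.7 | 10% | 15% |
| 0.2% | 13.0 vs 3.3 | 18% | 9% |

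**7. A benchmark for the all-infants comparison.** Suppose that the only mechanism is more births before 37 weeks, with equal case fatality by arm in each stratum. If s is the share of placebo-arm deaths that were preterm, the all-infants death RR would be s × 1.38 + (1 − s) × 0.98, where 0.98 = (1 − 0.0674)/(1 − 0.0488). That is 1.10, 1.18, 1.26, 1.34 and 1.38 at s = 0.3, 0.5, 0.7, 0.9 and 1.0 (assumed). A result clearly above 1.38 would need earlier preterm birth, higher preterm fatality or a direct effect.

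**The case against.** The strongest defence has four parts.

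- **The randomised comparison is kept.** SAP 5.4.1 retains the overall summary by arm. This stands. Whether an RR and interval go with it cannot be judged, because the method cells are redacted and SAP 10.2 places the table list in a separate document.
- **The term and preterm categories belong to the neonatal-death endpoint**, so readers need them as description. This stands, and it rules out removing or replacing the tables.
- **The term comparison is barely distorted by the mechanism described.** This stands for moderate risks (step 5). The weakness at term is too few expected deaths, not bias.
- **The case review is separate evidence.** It is, and it counts. But causes of death typical of prematurity do not show whether fatality among preterm infants was the same in both arms.

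A reader might go further and infer that the tables in the current SAP produced the statement in Protocol 2.3. The dates do not support that: the statement is in the amendment of 23 February 2023 and the SAP is dated 21 September 2023. SAP 7.1 says only that the Day 43 interim used methods similar to those of 5.4.1.

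A reader might also infer that the statement rests on a distorted preterm comparison. Protocol 2.3 cites no comparison of deaths by arm among preterm infants.

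**Conclusion.** The point holds in a limited form. The split is post-randomisation, and on the sponsor's own figures the vaccine shifts it, so the arms are not comparable within either stratum. About 28% of vaccine-arm preterm infants are excess. The possible distortion is material in the preterm stratum (0.72 to 1.28, in either direction) and small at term (1.00 to 0.93 for 1- to 5-fold risk). The finding of no excess at term is weak evidence for the separate reason that power for a doubling is about 6% to 18%. Taken with a qualitative review and no counts, it does not establish that the death imbalance is only a consequence of preterm birth.

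This does not show that the statement is wrong, or that the split has hidden a harm. With no death counts in either document, neither can be tested. The ranges assume one-directional shifting, the fatality ratios shown and the term mortality rates shown.

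**What to change.** - **SAP 5.4.1:** keep the term and preterm tables and add the footnote *post-randomisation split; not a randomised comparison*.
- **SAP 5.4.1:** add gestational age at vaccination (24 0/7–28 0/7; 28 1/7–34 0/7 weeks) as the baseline between-arm subgroup for infant safety. It is already a minimisation factor (Protocol 6.3.3) and already tabulated (SAP 5.1.1). It gives a valid subgroup comparison but will not show whether deaths run through prematurity.
- **Neonatal death:** base any conclusion on all infants, with counts, RR and 95% CI, read against the benchmark in step 7.
- **Study report, and Protocol 2.3 if it is next amended:** change the sentence to *may be a consequence of preterm birth; the term-only comparison cannot establish this*. An amendment for this sentence alone is not needed. If the firmer statement is wanted, support it with a mediation or principal-stratum sensitivity analysis.

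Cost: a few extra tables from data already collected, one footnote and a less firm statement.
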